7.6.3. Further Assessments

Treatment as Usual

• Treatment elements checklist

Qualitative Research

• Qualitative interviews to explore the perceived risks and benefits of taking olanzapine and participating in the trial.

Questions on RCT

• Willingness to take part in an RCT (double-blind)

For the justification of these data, see section 3. These selections of these assessments are the results of applying four times for this study to the NIHR HTA at stage 1 and two times at stage 2 and incorporating the feedback of the reviewers during six rounds of review into the trial design.

7.7 Trial assessments

Trial assessments will take place 8 weeks, 16 weeks, 6 months, and 12 months after baseline with an appointment of approximately 3 hours and will take place in person at trial sites. They include:

Clinical Examinations

- Psychiatric and physical examination
- Weight, height, blood pressure (BP), body temperature
- Laboratory parameters
- Body temperature
- Electrocardiogram (ECG)
- Treatment as Usual check
- Treatment elements checklist
- Concomitant Medications

Page 35 of 60

Adherence measures

- Olanzapine plasma level
- Pill count

Psychopathology

- Eating Disorder Examination-Questionnaire (EDE-Q)
- Depression Anxiety Stress Scales (DASS/RCADS)
- Revised Beliefs about Voices Questionnaire (BAVQ-R)
- Self-Regulation of Eating Behaviour Questionnaire (SREBQ)
- Yale-Brown Obsessive-Compulsive Scale (Y-BOCS/CY-BOCS)
- Columbia Suicide Severity Rating Scale (C-SSRS)

Rating and Documentation of Side Effects

- Epworth Sleepiness Scale (ESS/ESS-CHAD)
 - UKU- Side Effects Rating Scale (UKU-SERS)

Health Economy and Quality of Life

- EQ-5D-YTM
- Child, Adolescent and Adult Service Use Schedule (CAA-SUS)
- Eating Disorders Symptom Impact Scale (EDSIS)

Qualitative Research

- Experience of treatment and the trial, including motivation for adherence/nonadherence (after 16 weeks only)
- Carers/parents will be given an opportunity to contribute at the 16 week qualitative interview with the participants' consent.

Questions on RCT

• Willingness to take part in an RCT (double-blind; after 6 and after 12 months only)

For the justification of these data, see section 3. Section 3.7. provides an overview of all assessments and when they will take place.

7.8 Long term follow-up assessments

Beyond the trial assessment 12 months after baseline which is described above, no long-term follow-up assessments are planned.

7.9 Qualitative assessments

Patient experience of recruitment and treatment: Patient experience of recruitment and treatment, treatment acceptability and reasons for adherence or non-adherence will be ascertained in qualitative interviews which will be performed, transcribed, and analysed.

We will conduct individual qualitative interviews in a subgroup (N=30) of young people with AN who either agree (N=20) or decline (N=10) to participate in the OPEN feasibility study. Interviews will be

Page 36 of 60

conducted virtually or face-to-face based on the participants preference. Interviews will examine the decision-making process and the perceived risks and advantages of taking olanzapine within the study.

Those who are recruited to OPEN will be interviewed at baseline and after the 16-week assessment point about their experiences of olanzapine treatment, participating in the study, including beliefs about side effects, acceptability and adherence, the perceived burden of completing outcome measures and attitudes towards randomisation in a future clinical trial. We will interview people who have adhered to olanzapine as well as people who have dropped out. Patients who decline to participate in the main study but have consented to take part in the interviews will participate in one interview at baseline. The qualitative researcher will aim for 'empathic neutrality', posing open and non-leading questions that invite participants to recount their experiences of the study and treatment from their perspective.

Purposive sampling will be conducted based on gender, age, recruitment source, BMI at baseline and adherence to explore a range of perspectives.

Qualitative data will be analysed using the Framework Approach [85] to facilitate analysis within and between individual cases and groups of participants. The thematic framework will draw on a priori issues around the acceptability of the intervention and design study, but also be responsive to emergent themes. [name] will supervise a qualitative researcher who will get in contact with approached and recruited patients. All qualitative interviews in the UK will be carried out by the UK qualitative researcher (TBA). Qualitative data evaluation will be performed in cooperation with the qualitative research performed in [name] and [name] will consult with each other about the qualitative research performed in both countries.

7.10 Withdrawal criteria

The physician responsible for a patient can withdraw a patient from a trial or a certain aspect of the trial any time for appropriate medical reasons, be they individual adverse events or new information gained about a treatment. Trial participants also have the liberty to withdraw their consent at any time and for any reason.

A patient should stop olanzapine treatment if they show:

- If they show a QTc interval >500 ms in the ECG
- If they show rises by more than 60 msec from baseline [47] in the ECG
- Severe cardiac problems
- Serious Adverse Events (SAE) An SAE will be a withdrawal criterion if it is deemed to be related to the treatment with olanzapine by the Principal Investigator
- Serious Adverse Reaction (SAR)
- Suspected Unexpected Serious Adverse Reaction (SUSAR)

However, should a patient stop olanzapine, the patient is not necessary withdrawn from the study, every effort should be made to continue to obtain follow up data as long as the participant is willing.

The whole trial will stop in case of:

- A QTc interval >500 ms in the ECG or rises by more than 60 msec from baseline or other severe cardiac side effects in more than one patient
- Serious self-harm or suicidal behaviour in more than one patient. Serious self-harm is defined as the following:
 - Recent (within the last 12 months) self-harm with suicidal intent
 - Recent self-harm with the risk to a person's own life (e.g., drug intake, deep cutting, burning, swallowing sharp items)

• Recent self-harm which could lead, or has led, to long lasting impairment of one's health and functioning

7.11 Storage and analysis of clinical samples

No biological samples will be collected or stored for this trial. Laboratory parameters will only be determined as clinical routine laboratory parameters to ensure safety of the treatment as this is usually done in clinical practice.

7.12 End of trial

The trial will end after the database is locked following the 12 months-assessment of the 55th patient included into the study.

7.13 Safeguarding, Confidentiality and Distress Risk Management

7.13.1 Distress Risk Management

All of the questionnaires used in this study are routinely used in research studies and/or in the clinical setting. Similarly, clinical and qualitative interviews do include routinely used elements and approaches in research and/or clinical setting. Although the risk of major distress occurring during an interview (in association with the research study) is minimal considering the participants are known patients under specialist eating disorder services and based on previous research using similar procedures, there is a possibility that some of the questionnaires or the interview processes result in increased distress in the participants.

To minimise the risk, the participants will be given information about the study procedures (including but not limited to the questionnaires, the physical health checks and the qualitative interviews) in the participant information sheet and they will be provided with an opportunity to discuss their further concerns or queries with a clinician.

All the interviews and questionnaires are being completed at usual NHS clinical sites, by or in the presence of a research clinician. The Chief Investigator is a consultant psychiatrist with experience of working with vulnerable people. They and other research clinicians on the team will overview all procedures and be available during the sessions.

Members of the research team will remain sensitive to signs of participant distress and will terminate the procedure if the participant wishes to stop. Researchers will also check the participant's mental state and safety upon completion of the interview process at each encounter. A clinician will always be available on site to support if necessary. If there are ongoing concerns due to participant distress, the research team will liaise with the participant's clinical team to ensure there is ongoing clinical support available and if necessary, to discuss whether it is appropriate for the participant to remain in the study.

7.13.2 Safeguarding Management

Considering the specific vulnerabilities of the participants of this study, additional steps will be taken to ensure physical and mental safety of the participants throughout the trial. Firstly, all participants will be in the care of a GP and under an NHS specialist eating disorder team. Notably, for recruitment of

Page 38 of 60

participants to this study, the psychiatrists in the participating ED services will be identifying patients in their care for potential eligibility and informing them of the study. Participants who do not want to remain in the care of their specialist team will be withdrawn from the study and their GP informed. This will be explained to the participants in the participant information sheets and consent forms.

Similarly, consent for the research team to be in contact with the patient's care teams (including the ED specialist services and their GP) will be explicitly obtained from all patients at screening.

On the patient information sheets, the contact details of the trial manager are being shared with the participants as a contact person, aside from their clinical teams, that could be contacted by participants to discuss any concerns.

In case of a participant disclosing information relevant to their health and safety such as risk to self (eg. self-harming or suicidal risk), risk from others, or the safety of others, or any such information regarding the participant becoming apparent to the research team during the course of the study, the following steps will be taken and will be reflected on the patient information sheet and consent forms:

- Participants will be informed that all information is confidential, regardless of the participant's age, but there will be limits to confidentiality when there is a risk to self, from others, or to others. It will be explained to all participants that confidentiality might be broken when it is in the best interest of the participant or the public, or required by law. For participants under the age of 16, the threshold for disclosing risk to parents will take into consideration what is appropriate to the best interests of the child. As part of the study, the participants are being asked to comply with contraceptive measures and take regular pregnancy tests, if applicable. Participants will be explained that in case of a pregnancy, they will be withdrawn from the study and this information will be shared with themselves, their clinical team, and potentially with their parents/carers in case of a participant under the age of 16. In case of a safeguarding concern becoming apparent during the research process, the researcher will liaise with the participant's clinical team to raise the concern with them and to ensure that the local safeguarding process is being completed.
- In all cases of concern around a participant's health and safety, the researcher will liaise with the participant's responsible clinician at the ED services to assess the participant and advise on further actions, including whether the participant is able to remain in the study. Regardless of the participant's situation with regards to the study, they remain a patient under the specialist ED team, therefore, the local risk management policies of the relevant trust shall apply and be overseen by the clinical team of the patient.

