3.3.7. Drug safety measures

Adverse effects: In OPEN, we will measure possible adverse effects in a structured and standardised manner. As there are no existing guidelines concerning the use of antipsychotics in AN, we decided on the clinical outcome measures of adverse effects based on the World Federation of Societies of Biological Psychiatry (WFSBP) Guidelines for Biological Treatment of Schizophrenia [72].

- Physical examination:
 - Weight
 - Blood pressure (BP) and pulse
 - Body temperature
- Electrocardiogram (ECG): A QTc interval of > 450 ms confirmed by a second ECG measurement or an otherwise seriously abnormal ECG [47] will be an exclusion criterion for this study. We will only exclude patients if two separate readings are >450ms.
- A QTc interval >500 ms in the ECG or rises by more than 60 msec from baseline or other severe cardiac side effects will stop study participation of this patient.
- A QTc interval >500 ms in the ECG or rises by more than 60 msec from baseline or other severe cardiac side effects in more than one patient in the feasibility study will lead to a stop of the study after the feasibility phase.
- Laboratory parameters: Routine laboratory parameters in patients with AN often show alterations, including electrolytes, liver enzymes, kidney parameters, leukocyte count, haemoglobin and others. Additionally, medical problems secondary to AN, or due to the treatment itself may lead to further laboratory abnormalities [10]. Furthermore, olanzapine may lead to changes in metabolic parameters, including cholesterol, plasma glucose and blood fats [73]. Therefore, the following parameters will

Page 24 of 60

be determined at baseline, 8 weeks, 16 weeks (end of trial medication) and at the 12-month followup.

- Electrolytes and salt/water balance
- Kidney function
- Liver function
- Blood count/bone marrow
- Plasma glucose (fasting or random) or glycated hemoglobin (HbA1c) and lipid profile
- Pregnancy test in women and female adolescents

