7.1.2 Screening

The aim of the screening process is to ascertain whether inclusion and exclusion criteria are met. In accordance with the inclusion and exclusion criteria outlined in section 6.1. and 6.2., the clinical research team will update the eCRF with the following information about the potential participant after informed consent is obtained:

- Age
- Gender
- Diagnosis of AN
- Level of nonresponse to TAU (at least one month of treatment; weight gain <2 kg within at least one month of TAU; outpatients should have attended ≥4 therapeutic sessions.
- Potential serious self-harm, suicidality, psychotic disorder
- Serious medical comorbidities which are contraindications for olanzapine
- Current alcohol or illicit drug use disorder
- Use of major tranquilliser or opioids
- QTc time
- Liver function tests or white cell count
- Use of other medication at stable dose for <4 weeks
- Use of medication potentially interacting with olanzapine
- Pregnancy test, willingness to take further pregnancy tests after 8 weeks, 16 weeks, 6 months, and 12 months and to take contraceptive measures as specified in section 8.10. on trial restrictions (females of childbearing potential only)
- Breast feeding
- Capacity of the adult participant or the adolescent participant and their legal representatives to agree to the study

For definition of serious self-harm and serious medical comorbidities see section 6.1. and 6.2.

To obtain this information and thus determine inclusion and exclusion criteria, a full psychiatric and medical history taking, physical examination and assessment will take place. See section 6.1. and 6.2. To obtain this information is included in the standard care for a patient with AN if pharmacological treatment is considered.

Page 31 of 60

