9 PHARMACOVIGILANCE

9.1 Definitions

The Medicines for Human Use (Clinical Trials) Regulations 2004 and Amended Regulations 2006 gives the following definitions:

- Adverse Event (AE): Any untoward medical occurrence in a participant to whom a medicinal product has been administered, including occurrences which are not necessarily caused by or related to that product.
- Adverse Reaction (AR): Any untoward and unintended response in a participant to an investigational medicinal product which is related to any dose administered to that participant.
- **Unexpected Adverse Reaction (UAR)**: An adverse reaction the nature and severity of which is not consistent with the information about the medicinal product in question set out in:

The summary of product characteristics (SmPC) for that product (for products with a marketing authorisation)

- Serious adverse Event (SAE), Serious Adverse Reaction (SAR) or Suspected Unexpected Serious Adverse Reaction (SUSAR): Any adverse event, adverse reaction, or unexpected adverse reaction, respectively, that:
 - results in death;
 - is life-threatening;

- required hospitalisation or prolongation of existing hospitalisation;
- results in persistent or significant disability or incapacity;
- consists of a congenital anomaly or birth defect.
- **Important Medical Events (IME) & Pregnancy:** Events that may not be immediately lifethreatening or result in death or hospitalisation but may jeopardise the participant or may require intervention to prevent one of the other outcomes listed in the definition above should also be considered serious. Although not a serious adverse event, any unplanned pregnancy will also be reported. In case of a pregnancy, study medication will stop. The pregnant study participant will be followed up until 12 months after baseline.

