9.5 Overdose

Overdoses of 500 mg olanzapine tablets at once or 30 mg daily for at least one week have been reported. Therefore, we will define 500 mg olanzapine taken at once or 30 mg overdose for at least one week as overdose [87-93]. Overdoses will be observed from reported pill counts, patient comments and plasma level measurements. In case of an overdose, study medication will stop for this participant. However, they can remain in the study until 12 months after baseline. An overdose will be fully reported and described in an SAE report form.

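### Section 7.13.2 withdraws a pregnant participant from the study, while section 9.1 stops only the drug and follows her to 12 months; the QTc rules divide in a similar way

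*Protocol*

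**What the plan says.** **Pregnancy.** Protocol section 7.13.2, in a paragraph on confidentiality, says it will be explained to participants that "in case of a pregnancy, they will be withdrawn from the study". The same section says that its steps "will be reflected on the patient information sheet and consent forms". Section 9.1, under important medical events and pregnancy, says: "In case of a pregnancy, study medication will stop. The pregnant study participant will be followed up until 12 months after baseline". The event is foreseen. Section 7.1.2 asks at screening about "willingness to take further pregnancy tests after 8 weeks, 16 weeks, 6 months, and 12 months", and the schedule in 3.7 lists a pregnancy test at each of those visits.

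**Stopping olanzapine in general.** Section 7.10 lists reasons to stop the drug: QTc above 500 ms, a rise of more than 60 ms from baseline, severe cardiac problems, and serious events or reactions (an SAE counts if judged related to olanzapine). Pregnancy is not on the list. After it comes the general rule: "should a patient stop olanzapine, the patient is not necessary withdrawn from the study", and "every effort should be made to continue to obtain follow up data as long as the participant is willing".

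**QTc and cardiac findings.** Sections 3.3.7 and 6.2 use the same QTc thresholds but say that these or "other severe cardiac side effects will stop study participation of this patient".

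**Overdose.** Section 9.5 stops the drug and adds: "However, they can remain in the study until 12 months after baseline".

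**The concern.** Stopping a drug and leaving a study are different things, and this protocol distinguishes them in 7.10 and 9.5. For pregnancy it gives both instructions in different places.

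A site that acts on 7.13.2 ends the follow-up that 9.1 promises for someone exposed to olanzapine during pregnancy. A site that acts on 9.1 contradicts what 7.13.2 says the participant was told. The word withdrawn also has a consequence: under 7.2, data collected before withdrawal may be used only if the participant consented to that.

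The cardiac rules raise the same problem less sharply. A site following 3.3.7 or 6.2 ends follow-up that 7.10 asks it to pursue.

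The loss falls on assessments the trial exists to measure. Completion at the five assessment points is part of the primary objective (3.1), and 3.4 names 12 months as one of two important time points.

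**Working it through.** The main check is a comparison of texts. The arithmetic only gives the scale.

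**1. The rules side by side**

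| Event | Section | Drug | Study participation |
|---|---|---|---|
| Pregnancy | 7.13.2 | not stated | withdrawn |
| Pregnancy | 9.1 | stops | followed to 12 months |
| QTc / severe cardiac | 3.3.7, 6.2 | not stated | stops |
| QTc / severe cardiac | 7.10 | stops | not necessarily withdrawn; follow-up sought |
| Overdose | 9.5 | stops | can remain to 12 months |

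The pregnancy rows cannot both be followed literally. Section 7.10's general rule agrees with 9.1, and 9.5 is built the same way. Section 9.1 also calls her a study participant and ends her follow-up at 12 months after baseline, which 7.8 shows is the last planned assessment. That supports reading 9.1 as remaining in the study, although it does not say which assessments the follow-up contains.

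**2. Follow-up at stake for pregnancy**

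Inputs: test times from 7.1.2 and end of follow-up from 9.1, taking 6 months = 26 weeks and 12 months = 52 weeks.

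- Found at 8 weeks: 52 − 8 = 44 weeks under 9.1; 0 under 7.13.2 read literally.
- Found at 16 weeks: 52 − 16 = 36 weeks; 0.
- Found at 6 months: 52 − 26 = 26 weeks; 0.

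No count of lost visits is given, because 9.1 does not define the content of its follow-up.

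**3. Effect on completion**

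Input: N = 55 (sections 4 and 10.1). One participant withdrawn by rule who would otherwise have completed: 1/55 = 1.8 points. Two: 2/55 = 3.6 points.

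For scale, 10.1 states a 12.2-point margin for the adherence rate at 70%. The usual formula 1.96 × √(0.7 × 0.3 / n) gives 12.11 with n = 55 and 12.22 with n = 54, so the stated figure reproduces with n − 1. The conflict does not depend on it.

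**4. Effect on the questionnaire rule in 3.3.1**

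A questionnaire is dropped from the later application if more than 25% is not completed. Assuming the count is over all 55 participants, 25% of 55 = 13.75. So 13/55 = 23.6% keeps it and 14/55 = 25.5% drops it. One extra withdrawal changes the decision only if the count would otherwise be exactly 13.

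**5. How likely is the event?**

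The protocol gives no pregnancy or QTc rate. Assuming a common 12-month pregnancy probability r for all 55 participants, the chance of at least one is 1 − (1 − r)^55:

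| r | Expected cases (55r) | Chance of at least one |
|---|---|---|
| 0.5% | 0.3 | 24% |
| 1% | 0.6 | 42% |
| 2% | 1.1 | 67% |
| 5% | 2.8 | 94% |

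These rates are illustrative, and treating all 55 as at risk overstates the chance if some are not of childbearing potential.

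**The case against.** **The two pregnancy sentences serve different purposes.** One concerns confidentiality and the other pharmacovigilance, so 9.1 may mean only safety follow-up of the pregnancy. Section 7.10 lets a physician withdraw a patient from one aspect of the trial, so withdrawal need not be total. Section 9.2 monitors events to 13 months after baseline and keeps SAE reporting open after a participant withdraws consent to data processing. This softens the conflict without removing it. Neither section names pregnancy, 9.1 says a pregnancy is not itself a serious adverse event, and no text says that safety follow-up survives withdrawal under 7.13.2.

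**The QTc texts can be read together.** The sentence in 7.10 is permissive, so 3.3.7 and 6.2 could be its specific exceptions. That is why this part ranks second. Still, 7.10 names the same QTc thresholds at the head of the list to which the sentence applies, and makes no exception for them.

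The reach of the QTc rule is also limited. Under 6.2 and 7.10 a second such patient stops the whole trial, and 9.3 then ends data collection for everyone. On that reading the individual rule matters for at most one participant, or 1.8 points. (Section 3.3.7 places the stop after the feasibility phase.)

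**The safeguarding section has a history.** The amendment history says it was added in version 1.1 on the ethics committee's recommendation, so the sponsor may prefer to change 9.1. That is a legitimate choice, but one of the two texts must still change.

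**The numbers are small.** This is accepted. No imputation is planned (10.7), and missing data are themselves informative here.

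**Conclusion.** The concern holds: the rules are wrong as written. For pregnancy, 7.13.2 and 9.1 give incompatible instructions in current text, and nothing else in the protocol settles which applies. For QTc and severe cardiac findings, 3.3.7 and 6.2 conflict with 7.10 less firmly.

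The practical cost is up to 44 weeks of follow-up lost for a participant whose pregnancy is found at the 8-week test. The statistical cost is minor: on an assumed 0 to 2 participants affected, 0 to 3.6 points of completion. No material bias is claimed.

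The information sheet and consent forms were not available, so whether they repeat the withdrawal sentence is unknown. The change should be made because sites need one instruction at a safety event, and because follow-up after drug exposure should not be lost to a drafting conflict.

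**What to change.** - **7.13.2:** say that olanzapine stops on pregnancy and that follow-up continues to 12 months after baseline while she consents, as in 9.1. If the sponsor intends safety follow-up only, say so in both 7.13.2 and 9.1 and state what it contains.
- **7.10:** add pregnancy to the reasons for stopping olanzapine.
- **3.3.7 and 6.2:** replace the statement that participation ends with one that olanzapine stops and follow-up continues under 7.10 while the participant is willing.
- **Information sheet and consent forms:** make the matching correction if they carry the 7.13.2 sentence.

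**Cost:** wording changes in four sections, and in 9.1 as well if safety-only follow-up is chosen. If the sponsor treats the change as substantial, section 12.10 requires notice to the ethics committee. The main option adds no follow-up beyond what 9.1 and 7.10 already call for.
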